5.10 Availability of investigational medicinal product after termination of study

There is no option to continue study treatment once the study subject has completed or discontinued the study.

6. STUDY PROCEDURES AND ASSESSMENTS

6.1 Study procedures

Table 3 lists all study procedures and indicates with an 'x' during which visit a particular procedure is performed.

Table 3. Schedule of study events

Protocol activities	Screening	Treatment period						End-of-study
	≤21 days before first dose	Day -1	Day 1	Days 2-5	Day 6	Day 7	Day 8	4-21 days from last dose
IC ¹								
Physical examination	X							X
Demography and substance use	X							
Use of nicotine	X	X						
Weight and BMI	X							X
Height	X							
Vital signs: BP and HR	X	X	X ²		X ³	X ⁴		X
12-lead ECG	X	X	X ^{2,5}		X ⁶	X ⁷		X
Laboratory assessments								
• Haematology and clinical chemistry	X		X ^{2,8}			X ⁸		X ⁹
• Urinalysis	X		X ²			X		X
• Serology	X							
Alcohol breath test	X	X						
Urine drug abuse test	X	X						
C-SSRS	X					X		
Decision of entry	X							
Study treatments, 4 times a day								
Carbidopa					X			
ODM-104					X ¹⁰			
Levodopa						X		
Blood samples for PK						X	X	
Blood sample for PG								X ¹¹
Medical history and current medical conditions								Continuously
AEs								Continuously
Concomitant treatments								Continuously

¹ IC for the main study before any screening activities; for the optional PG IC, see footnote 11

² On day 1: 0-2 h before the first dose

Vital signs in supine position after 5 min rest:

³ On day 6: 1-2 h after the 7 h dose

⁴ On day 7: 0-2 h before the first dose and at 1-2 h after the 7 h dose

12-lead ECG in supine position after 5 min rest

⁵ On day 1: 0-2 h before the first dose - 3 recordings within 5 min, 1-2 min interval between the measurements

⁶ On day 6: 1-2 h after the 7 h dose

⁷ On day 7: 0-2 h before the first dose and 1-2 h after the 7 h dose

⁸ Selected laboratory tests before the first dose of the day

⁹ The same laboratory tests as at the screening visit except thyroid stimulating hormone and albumin

¹⁰ Only in treatment periods including ODM-104

¹¹ PG (optional): The sample is taken once from subjects who have signed the PG IC

C-SSRS = Columbia-Suicide Severity Rating Scale; PG = pharmacogenomics

6.1.1 Procedures during the screening period

Screening procedures will start after receiving approval from the ethics committee (EC) and competent authority (CA).

A prospective subject will receive both written and verbal information about the study and will have an opportunity to ask questions and sufficient time to decide whether or not to participate in the study. A signed and dated written IC for the main study will be obtained prior to any screening activities (see section 11.3). A separate pharmacogenomic (PG) IC will be obtained from subjects who agree to take part in the optional study-related exploratory PG study (see section 6.3).

The screening visit will take place within 21 days before the first study treatment administration.

The following procedures will be performed at the screening visit:

- Physical examination will be performed.
- Demographic data (sex, year of birth, age and racial group), substance use (use of nicotine, alcohol and caffeine, and drug abuse) and weight, height and BMI will be recorded.
- Medical history, current medical conditions and concomitant treatments will be recorded.
- AEs will be recorded.
- BP and HR will be recorded in the supine position after at least 5 min rest.
- 12-lead ECG will be recorded in the supine position after at least 5 min rest.
- Alcohol breath testing will be performed.
- Blood samples for haematology, clinical chemistry and serology will be collected after fasting for at least 10 h; see section 6.4.5 for details.
- Urine drug abuse testing will be performed.
- Urinalysis will be performed.
- Columbia-Suicide Severity Rating Scale (C-SSRS) will be performed.
- Subjects will be instructed to call the study centre when they experience AE or need to take concomitant treatment after the screening visit until the end-of-study visit when they are not in-house.

For practical reasons, the procedures outlined above may be performed on 2 separate occasions, for example, the physical examination may be performed a couple of days later than the other procedures.

A subject will be entered into the study if all of the inclusion criteria and none of the exclusion criteria are met and will be randomised to one of the treatment sequences before starting study treatments.

6.1.2 Procedures during the treatment periods

6.1.2.1 Days -1 and 1

Subjects will arrive at the study centre in the evening before day 1 (day -1) and stay at the study centre until the 24 h PK blood sample has been collected in the morning of day 8.

The following procedures will be performed on day -1:

- Alcohol breath and urine drug abuse tests will be performed before the first study treatment administration. Use of nicotine-containing products within the previous week will be enquired.
- BP and HR will be recorded in the supine position after at least 5 min rest.
- 12-lead ECG will be recorded in the supine position after at least 5 min rest.

The following procedures will be performed on day 1:

- BP and HR will be recorded in the supine position after at least 5 min rest 0-2 h before the first morning dose.
- 12-lead ECG will be recorded in the supine position after at least 5 min rest 0-2 h before the first dose. 3 recordings will be performed within 5 min (1-2 min interval between the measurements).
- Blood samples for selected haematology and clinical chemistry tests will be collected before the first dose; see section 6.4.5.
- Urinalysis will be performed before the first dose.
- Subjects will take carbidopa and ODM-104 (in study periods including ODM-104) as described in section 5.3.
- Meals will be served as described in section 5.3.
- Current medical conditions and concomitant treatments will be recorded.
- AEs will be recorded.

6.1.2.2 Days 2-5

The following procedures on days 2-5 will be performed:

- Subjects will take carbidopa and ODM-104 (on study periods including ODM-104) similar to day 1 and as described in section 5.3.
- Meals will be served as described in section 5.3.
- AEs, current medical conditions and concomitant treatments will be recorded.

6.1.2.3 Day 6

The following procedures on day 6 will be performed:

- Subjects will take carbidopa and ODM-104 (on study periods including ODM-104) similar to day 1 and as described in section 5.3.
- HR and BP will be recorded in the supine position after at least 5 min rest 1-2 h after the 7 h dose.
- 12-lead ECG will be recorded in the supine position after at least 5 min rest 1-2 h after the 7 h dose.
- Meals will be served as described in section 5.3.
- Current medical conditions and concomitant treatments will be recorded.
- AEs will be recorded.

6.1.2.4 Day 7

Subjects will fast from 22:00 h (10 h) on day 6 until breakfast on day 7, except that drinking of water is permitted up to 1 h before dose.

- BP and HR will be recorded in the supine position after at least 5 min rest 0-2 h before the first dose and 1-2 h after the 7 h dose.
- 12-lead ECG will be recorded in the supine position after at least 5 min rest 0-2 h before the first dose and 1-2 h after the 7 h dose.
- Blood samples for selected haematology and clinical chemistry tests will be collected before the first dose; see section 6.4.5 for details.
- Urinalysis will be performed.
- C-SSRS will be performed.
- Subjects will take the first dose (levodopa, carbidopa and possible ODM-104) approximately at 8:00 h after the pre-dose PK blood sampling. All study treatments will be taken precisely at the planned time points, including time points coinciding with PK blood sampling; see section 5.3 for details.
- Blood samples for PK assessments will be collected; see section 6.2.1 for details.
- Meals will be served as described in section 5.3.
- AEs, current medical conditions and concomitant treatments will be recorded.

6.1.2.5 Day 8

- Blood sample for 24-h PK assessments will be collected in the morning of day 8; see section 6.2.1 for details.
- Subjects will be instructed to call the study centre when they experience any AE or need to take any concomitant treatment until the end-of-study visit when the subjects are not in-house.
- Subjects can leave the study centre after the 24 h PK blood sample has been collected.

6.1.3 Procedures during the end-of-study visit

The end-of-study visit will take place 4-21 days after the last study treatment dose. The following procedures will be performed at the end-of-study visit:

- Physical examination will be performed. Weight will be measured and BMI recorded.
- BP and HR will be recorded in the supine position after at least 5 min rest.
- 12-lead ECG will be recorded in the supine position after at least 5 min rest.
- Blood samples for haematology and clinical chemistry tests will be collected. The same haematology and clinical chemistry tests as at the screening visit except thyroid stimulating hormone and albumin will be determined; see section 6.4.5 for details.
- Urinalysis will be performed.
- AEs, current medical conditions and concomitant treatments will be recorded.

6.2 Pharmacokinetic assessments

6.2.1 Blood sampling

Peripheral venous blood samples will be drawn for the determination of concentrations of levodopa, carbidopa, 3-OMD and ODM-104 in plasma. For blood sampling, a forearm vein will be cannulated. Blood samples will be drawn before the drug administration (0 h) and at 0.5, 1, 1.5, 2, 2.5, 3, 3.5, 4, 4.5, 5, 5.5, 6, 6.5, 7, 7.5, 8, 8.5, 9, 9.5, 10, 10.5, 11, 11.5, 12, 12.5, 13, 13.5, 14, 15, 16 and 24 h after the drug administration. At time points 3.5, 7 and 10.5 h, the study treatment will be administered and the blood sample drawn at a same time. However, exact timing of study treatment administration will be prioritised, e.g. in case of problems in blood sampling.

Before the start of the study, detailed instructions for collecting, handling, storing and shipping of the plasma samples will be provided to the study centre. Maximum volume of blood collected in the study is provided in the subject information.

6.2.2 Determination of drug concentrations

The concentrations of levodopa, carbidopa, 3-OMD and ODM-104 in plasma will be determined with validated LC-MS/MS methods. Metabolites of ODM-104 will be determined, if indicated necessary by the PK results of the study. Bioanalytical details and criteria for acceptance of the results will be described in the bioanalytical plans and reported in bioanalytical reports.

6.2.3 Calculation of pharmacokinetic variables

Table 4 lists the PK parameters which will be derived from the concentration-time data of levodopa, carbidopa, 3-OMD and ODM-104.

Table 4. PK parameters to be calculated for levodopa, carbidopa, 3-OMD and ODM-104

Parameter	Levodopa	Carbidopa	3-OMD	ODM-104
C_{max}	X ¹	X ¹	X ¹	X ¹
$C_{max,tau}$	X ¹			X
t_{max}	X	X	X	X
$t_{max,tau}$	X			X
$C_{min,tau}$	X ¹			X
$C_{min,tau,actual}$	X ¹			
AUC_{tau}	X ¹			X
AUC_{0-16}	X ¹			
AUC_{0-24}	X ¹	X ¹	X ¹	X ¹
AUC_{∞}	X			X
$t_{1/2}$	X			X
λ_z	X			X
$C_{max}/C_{min,tau}$	X ¹			
$C_{max}/C_{min,tau,actual}$	X ¹			
$C_{max}/C_{(16h)}$	X ¹			
PTF_{tau}	X ¹			
PTF_{0-16h}	X ¹			

¹ Statistical analysis will be performed

C_{max}	The maximum observed concentration of the concentration-time curve
$C_{max,tau}$	The maximum observed concentration for each dosing interval
t_{max}	The time to reach the maximum observed concentration
$t_{max,tau}$	The time to reach the maximum observed concentration for each dosing interval
$C_{min,tau}$	The observed concentration at the end of each dosing interval i.e. concentration at 3.5 h, 7 h, 10.5 h and 14 h
$C_{min,tau,actual}$	The observed minimum plasma concentration after each dose before the concentration starts to rise due to the following dose. For the 4th dosing interval, the plasma concentration at time 16 h will be used as the minimum plasma concentration.
AUC_{tau}	The area under the concentration-time curve calculated with linear trapezoidal rule for each dosing interval
AUC_{0-16}	The area under the concentration-time curve calculated with linear trapezoidal rule from time 0 to the 16 h PK sample
AUC_{0-24}	The area under the concentration-time curve calculated with linear trapezoidal rule from time 0 to the 24 h PK sample
AUC_{∞}	The area under the concentration-time curve from time 0 to infinity, AUC_{∞} will be determined by adding area under the concentration-time curve from time 0 to the last sample with a quantifiable concentration (AUC_t) to the extrapolated area that will be

	determined by dividing the last quantifiable concentration by λ_z
$t_{1/2}$	The terminal elimination half-life that is calculated with the equation $\ln 2 / \lambda_z$
λ_z	The terminal elimination rate constant from the log-linear portion of the concentration-time curve after the last (10.5 h) dose
$C_{\max}/C_{\min,\tau}$	Ratio of the maximum observed concentration in each dosing interval and the observed concentration at the end of each dosing interval
$C_{\max}/C_{\min,\tau,\text{actual}}$	Ratio of the maximum observed concentration in each dosing interval and the observed minimum plasma concentration after each dose before the concentration starts to rise due to the following dose. For the 4th dosing interval the plasma concentration at time 16 h was used as the minimum plasma concentration
$C_{\max}/C(16\text{h})$	Ratio of the maximum observed concentration from time 0 to 16 h and the observed concentration at time 16 h
PTF_{τ}	Peak-trough fluctuation for each dosing interval, calculated by $(C_{\max,\tau} - C_{\min,\tau}) \times 100 / C_{\text{av},\tau}$, where the average concentration, $C_{\text{av},\tau} = \text{AUC}_{\tau} / \text{duration of dose interval}$
PTF_{0-16}	Peak-trough fluctuation, calculated by $(C_{\max} - C_{\min}) \times 100 / C_{\text{av}}$, where the average concentration, $C_{\text{av}} = \text{AUC}_{0-16} / 16 \text{ h}$

The PK parameters will be calculated with non-compartmental methods using PhoenixTM WinNonlin[®] Build 6.3.0.395 or a later software version (Certara L.P., USA). The actual time of sampling will be used in the calculation of PK parameters. Possible outlying concentrations excluded from the PK analysis will be reported and justified in the study report.

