5.3 Selection and timing of doses

Overall, MR levodopa strength will be 50, 100 or 150 mg, carbidopa strength will be 12.5, 25 or 65 mg and ODM-104 strength will be 0, 50 mg or 100 mg. Sinemet contains 100 mg of IR levodopa and 25 mg of carbidopa.

The strength of levodopa, carbidopa and ODM-104 will depend on the parallel group (Groups 1-4) the study subject has been assigned to. The doses during the 4 treatment periods are presented in [Table 1](#) in section [3.2](#).

In all parallel groups, depending on the treatment period, carbidopa with or without ODM-104 will be taken 4 times a day during the days 1-6. On day 7 (PK sampling day), carbidopa with or without ODM-104 will be taken at the same time with levodopa 4 times a day. The duration of treatment will be 7 days for carbidopa and ODM-104 and 1 day for levodopa. In one of the periods in Group 4, Sinemet will be taken on day 7 without ODM-104 and on days 1-6, only carbidopa 25 mg will be administered.

The selected strengths and dosing regimens are based on previous PK studies in healthy subjects conducted during ODM-104 development program and other levodopa programs.

Carbidopa and ODM-104 (in treatment periods including ODM-104) will be taken 4 times a day – first dose, 3.5 h, 7 h and 10.5 h doses, for 6 days. The study treatments should be taken

at the same time every day to provide even concentrations of the active ingredients. The recommended study treatment intake times on days 1-6 are 8:00, 11:30, 15:00 and 18:30 h.

Subjects will arrive at the study centre in the evening before day 1 (day -1) and stay at the study centre until the 24 h PK blood sample has been drawn in the morning of day 8. Subjects will take all study treatments at the study centre.

In the evening of day 6, subjects will start fasting for at least 10 h (from around 22:00 h on day 6) before the first morning dose (0 h) at approximately 8:00 h on day 7. Drinking of water is permitted until 1 h before dosing.

The recommended study treatment intake times on day 7 are the same as those on the previous 6 days: 8:00, 11:30, 15:00 and 18:30 h. Study treatments will be ingested with 200 ml of water. Study subjects should maintain an upright position (sitting or standing) for at least 1 h after the study treatment administration and as much as possible during the day until 24:00 h.

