| Table 14.2.2.1    | Carbidopa concentrations (ng/ml)                                 |
| Table 14.2.2.2.1  | AUC0-24 (h*ng/mL) of Carbidopa                                   |
| Table 14.2.2.2.2  | Statistical analysis for AUC0-24 (h*ng/mL) of Carbidopa          |
| Table 14.2.2.3.1  | Cmax (ng/ml) of Carbidopa  |
| Table 14.2.2.3.2  | Statistical analysis for Cmax (ng/ml) of Carbidopa               |
| Table 14.2.2.4    | tmax (h) of Carbidopa  |
| Table 14.2.3.1    | 3-ODM concentrations (ng/ml)                                     |
| Table 14.2.3.2.1  | AUC0-24 (h*ng/mL) of 3-ODM                                       |
| Table 14.2.3.2.2  | Statistical analysis for AUC0-24 (h*ng/mL) of 3-ODM              |
| Table 14.2.3.3.1  | Cmax (ng/ml) of 3-ODM  |
| Table 14.2.3.3.2  | Statistical analysis for Cmax (ng/ml) of 3-ODM                   |
| Table 14.2.3.4    | tmax (h) of 3-ODM  |
| Table 14.2.4.1    | ODM-104 concentrations (ng/ml)                                   |
| Table 14.2.4.2    | AUC0tau (h*ng/mL) of ODM-104                                     |
| Table 14.2.4.3    | AUC0-24 (h*ng/mL) of ODM-104                                     |
| Table 14.2.4.4    | Statistical analysis of AUC0-24 (h*ng/mL) of ODM-104             |
| Table 14.2.4.5    | AUCinf (h*ng/mL) of ODM-104                                      |
| Table 14.2.4.6    | Cmax,tau (ng/ml) of ODM-104                                      |
| Table 14.2.4.7    | Cmax (ng/ml) of ODM-104  |
| Table 14.2.4.8    | Statistical analysis of Cmax (ng/ml) of ODM-104                  |
| Table 14.2.4.9    | Cmin,tau (ng/ml) of ODM-104                                      |
| Table 14.2.4.10   | tmax,tau (h) of ODM-104  |
| Table 14.2.4.11   | tmax (h) of ODM-104  |
| Table 14.2.4.12   | t½ (h) of ODM-104  |
| Table 14.2.4.13   | Lambda z of ODM-104  |

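### AUC∞ for ODM-104 starts on day 7 after six days of dosing, so this one descriptive parameter includes carry-over and is not comparable with levodopa AUC∞

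*Protocol*

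**What the plan says.** Protocol section 6.2.3 defines AUC∞ once, as "The area under the concentration-time curve from time 0 to infinity". It is the area up to the last quantifiable sample plus an extrapolated part "determined by dividing the last quantifiable concentration by λ_z". Table 4 marks the parameter for levodopa and for ODM-104. SAP Table 2 (section 8.4) lists it for the same two analytes by name, without a formula. The SAP output list gives it a descriptive table, 14.2.4.5, titled "AUCinf (h*ng/mL) of ODM-104".

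Protocol section 5.3 fixes the clock and the dosing history:

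- Time 0 is the "first morning dose (0 h) at approximately 8:00 h on day 7".
- Before that, "carbidopa with or without ODM-104 will be taken 4 times a day during the days 1-6", at the "first dose, 3.5 h, 7 h and 10.5 h doses, for 6 days".
- In total, "The duration of treatment will be 7 days for carbidopa and ODM-104 and 1 day for levodopa".

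Section 6.2.1 takes samples only from before the first day 7 dose up to 24 h. There is no day 1 profile. Neither document mentions a pre-dose correction, or a caveat that the ODM-104 value includes drug from earlier days.

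For ODM-104, Table 4 marks only Cmax and AUC0-24 for statistical analysis. AUC∞ is summarised descriptively.

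**The concern.** For levodopa the definition is sound: the first dose of the period falls at time 0, so the area to infinity is the exposure from the four day 7 doses. For ODM-104 the curve starts on top of whatever remains from days 1-6. Integrating to infinity collects the whole area of the four day 7 doses and also the remaining area of the earlier ones. One name and one formula thus yield two different quantities.

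The PK of ODM-104 after repeated administration is a secondary objective (Protocol section 2.2), so this is a reported result. A reader of Table 14.2.4.5 could fairly take it as the exposure from a day's doses, as it is for levodopa. The discrepancy runs in one direction and varies between subjects with their half-life. Carbidopa, which follows the same seven-day schedule, has AUC0-24 but no AUC∞ in Table 4.

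**Working it through.** The documents state no carry-over figure and no ODM-104 half-life, so there is no planned figure to reproduce. The direction follows from the definition and the schedule under linear kinetics. The size has to be shown as a range.

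**Inputs from the Protocol**
- Dose times within a day: 0, 3.5, 7 and 10.5 h (section 5.3).
- ODM-104 doses before time 0: 6 days × 4 = 24. The last falls 24 − 10.5 = 13.5 h before time 0.
- λz comes from the decline after the 10.5 h dose (section 6.2.3).

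**Assumptions**
- Linear kinetics and mono-exponential decline with rate k = ln 2 / t½.
- Half-lives of 2 to 12 h, for illustration only. Section 1.1 says that elimination in animals is longer than that of entacapone, which does not fix a human value.

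**Formula**

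A dose given u hours before time 0 still has the fraction exp(−ku) of its area to come. A dose at clock time q, d days before day 7, has u = 24d − q. Relative to the area of the four day 7 doses:

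excess = G × S, where
- G = mean of exp(kq) over q = 0, 3.5, 7, 10.5
- S = sum of exp(−24kd) over d = 1 to 6

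**Worked case, t½ = 6 h**
- exp(kq) = 1, 1.498, 2.245 and 3.364, so G = 2.027.
- exp(−24k) = 2⁻⁴ = 0.0625, so S = 0.0667.
- Excess = 2.027 × 0.0667 = 13.5%.

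**Range**

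| Assumed t½ (h) | G | S | Excess of AUC∞ over the four day 7 doses |
|---|---|---|---|
| 2 | 13.43 | 0.00024 | 0.3% |
| 3 | 4.90 | 0.0039 | 1.9% |
| 4 | 3.09 | 0.0159 | 4.9% |
| 6 | 2.03 | 0.0667 | 13.5% |
| 8 | 1.67 | 0.1429 | 23.8% |
| 12 | 1.39 | 0.3333 | 46.3% |

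**Checks**
- *Absorption.* With first-order absorption (ka = 2/h, assumed) the excess is 0.4%, 2.2%, 5.4%, 14.3%, 24.9% and 47.7% for the same half-lives. The conclusion does not depend on instant input.
- *AUC0-24 as the alternative.* In the same model with absorption, true day 7 AUC0-24 divided by the area of one day's doses is 1.00 at every half-life in the table. On the Protocol's sampling times with linear trapezoids the ratio is 1.00 to 1.02. By day 7, what the day inherits from earlier doses balances what its own doses leave beyond 24 h.
- *Dose.* G and S depend on k and the dose times, not on the amount given. Under linear kinetics the proportional excess is the same at 50 mg and 100 mg.

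**The case against.** The strongest reply is that the formula returns exactly what the Protocol says it returns, the area from time 0 to infinity. No section says that ODM-104 AUC∞ stands for the exposure of one day's doses. SAP section 7.1 mentions AUC∞ only as an example of a parameter covering the whole of day 7, to set a rule for emesis. The parameter is descriptive, and the suitable measures are already planned: AUCtau, and AUC0-24 with both a descriptive and a statistical table. With no half-life in the documents, the effect may be negligible.

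Most of this stands and limits the severity. It does not remove the point. The same name and formula still carry two meanings in one parameter table, and nothing tells the reader so.

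Three stronger readings are tempting, and the documents do not support them:

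- **A biased ODM-104 dose choice.** Section 1.2 puts the primary focus on levodopa PK, and under linear kinetics the 50 versus 100 mg ratio of ODM-104 AUC∞ is essentially unchanged.
- **Biased clearance, accumulation or exposure-margin figures.** None is planned in Protocol Table 4, SAP Table 2 or the SAP output list.
- **A tail counted twice.** At steady state the excess equals the extrapolated area beyond 24 h in size. But the carry-over and the day 7 tail are different areas, each integrated once.

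**Conclusion.** The point holds, at low severity. Under linear kinetics ODM-104 AUC∞ as defined equals the AUC of the four day 7 doses plus the residual area of the earlier doses. It exceeds one day's exposure and is not comparable with levodopa AUC∞.

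The size is not determined by the documents. In the assumed model it is about 2% or less for half-lives up to 3 h, passes 10% between 4 and 6 h, and reaches about 46% at 12 h. These figures rest on linear kinetics, mono-exponential decline and an assumed half-life.

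The consequence is confined to the ODM-104 AUC∞ row and its descriptive table, 14.2.4.5. The primary levodopa AUC0-24 and every planned statistical analysis are unaffected.

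**What to change.** Remove AUC∞ for ODM-104 from Protocol Table 4, SAP Table 2 and SAP Table 14.2.4.5. Use the already planned ODM-104 AUC0-24 as the daily exposure after repeated dosing. Keep AUC∞ for levodopa.

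If an infinity value for ODM-104 is wanted, there are two options:

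- Subtract C(0 h)/λz, using the existing pre-dose sample. State that this assumes linear kinetics and a 0 h concentration already on the terminal slope. Since no samples are taken between 16 and 24 h, λz may rest on few late points, so the correction needs that caution.
- Leave the calculation as it is and label the parameter, in both tables and in the output, as including carry-over from days 1-6.

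The cost is wording in two parameter tables and one output fewer, or one subtraction or footnote. No samples or subjects are added.

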8.4.3 Pharmacokinetic analysis

The primary variable for the evaluation of PK of levodopa is AUC_{0-24} to describe the total levodopa exposure. The secondary PK variable is $C_{min,tau}$, which is used to describe minimum concentration during the dosing intervals. The ratio of the C_{max} in a dosing interval and the observed concentration at the end of the dosing interval, $C_{max}/C_{min,tau}$, which is used to describe levodopa fluctuation during the dosing intervals and other PK variables of levodopa, 3-OMD, carbidopa and ODM-104 will be evaluated as other variables.

PK parameters will be analysed after logarithmic transformation and 90% confidence intervals (CIs) for the geometric means will be calculated.

The conclusions regarding possible differences between different study treatments will be based on both overall evaluation of levodopa concentration-time profiles and formal statistical analyses of PK parameters.

Primary pharmacokinetic evaluation

The primary PK variable will be summarised using descriptive statistics by treatment and analysed using a mixed linear model with 90% CI applicable for the crossover design. The statistical model will include treatment and period as fixed effects and subject as random effect. Sensitivity analysis adjusted for subject weight and age will be performed.

Levodopa fluctuation ratios ($C_{\max}/C_{\min,\tau}$, $C_{\max}/C_{(16\text{ h})}$, PTF_{τ} and PTF_{0-16}), and AUC_{0-24} , C_{\max} and $C_{\min,\tau}$ will be the main PK variables of interest.

The primary conclusions will be based on the PP population.

Secondary pharmacokinetic evaluation

Statistical evaluation for secondary PK variable will be done using similar methods as for primary variable. Statistical model for $C_{\min,\tau}$ will include treatment, period, dosing interval, and treatment by dosing interval interaction as fixed effect and subject by period interaction as random effect.

Other pharmacokinetic evaluations

The other PK variables for the evaluation of PK of levodopa, carbidopa, 3-OMD and ODM-104 are presented in [Table 4](#). All PK variables will be summarised by treatment using descriptive statistics. Selected PK variables will be analysed using similar models and sensitivity analysis to the primary and secondary PK variables. Drug concentrations will be tabulated by time and treatment with descriptive statistics.

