#### 8.4.3 Additional variables

The ratio of the maximum observed concentration ( $C_{\max}$ ) in a dosing interval and the observed concentration at the end of the dosing interval,  $C_{\max}/C_{\min,\tau}$ , which is used to describe levodopa fluctuation during the dosing intervals and other PK variables of levodopa, 3-OMD, carbidopa and ODM-104 will be evaluated as additional variables.

Levodopa fluctuation ratios ( $C_{\max}/C_{\min,\tau}$ ,  $C_{\max}/C_{(16\text{ h})}$ ,  $PTF_{\tau}$  and  $PTF_{(0-16)}$ , and  $AUC_{0-24}$ ,  $C_{\max}$  and  $C_{\min,\tau}$ ) will be the main PK variables of interest.

Drug concentrations will be tabulated by time and treatment with descriptive statistics.

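### PTFtau is exactly 0 when an interval's highest sample is its last, so the planned log analysis can lose the flattest MR intervals; it also has no actual-trough version

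*Protocol*

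**What the plan says.** Table 4 in Protocol 6.2.3 gives PTFtau as "Peak-trough fluctuation for each dosing interval, calculated by" (Cmax,tau − Cmin,tau) × 100 / Cav,tau, with Cav,tau equal to AUCtau divided by the interval length. Cmax,tau is "The maximum observed concentration for each dosing interval". Cmin,tau is "The observed concentration at the end of each dosing interval i.e. concentration at 3.5 h, 7 h, 10.5 h and 14 h". Protocol 6.2.1 has the samples at 3.5, 7 and 10.5 h drawn as the next dose is given.

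The same table has a second trough, Cmin,tau,actual: "The observed minimum plasma concentration after each dose before the concentration starts to rise due to the following dose". It adds: "For the 4th dosing interval, the plasma concentration at time 16 h will be used as the minimum plasma concentration". The Cmax/Cmin ratio comes in both versions, one on each trough, and both are marked for statistical analysis in Protocol Table 4 and SAP Table 2. PTFtau is also marked, but exists only on Cmin,tau.

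Protocol 8.4.3 states: "PK parameters will be analysed after logarithmic transformation and 90% confidence intervals (CIs) for the geometric means will be calculated". It makes no exception for PTFtau. SAP 7.2.9 is looser: it commits to the log scale for at least AUC and Cmax and does not name PTFtau. SAP 8.4.3 says that a set including Cmax/Cmin,tau and PTFtau "will be the main PK variables of interest". Cmax/Cmin,tau,actual is not in that set.

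**The concern.** There are two separate weaknesses.

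**Zeros on a log scale.** PTFtau can be exactly 0, and the log of 0 does not exist. A zero arises when the profile is still rising at the end of the interval. That is plausible for a slow-release capsule and not for a fast tablet. The lost records would therefore be the flattest MR intervals, missing because of their value.

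**No actual-trough version.** If absorption starts with a lag, concentrations go on falling after the next dose, and the end-of-interval sample sits above the true trough. Table 4 provides for this in the ratio but not in PTFtau.

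The case for the MR product in Protocol 1.1 is a more stable plasma profile than Sinemet, and fluctuation is one of the things the study sets out to assess. A fluctuation measure that loses or shrinks values according to the shape of the profile bears on that reading. It matters most in Group 4, the only group with Sinemet, with 14 subjects planned.

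**Working it through.** The documents state no fluctuation figure, so there is nothing to reproduce. The first step is algebra on the definitions. The others are illustrations under assumed kinetics.

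**1. The zero case (no assumptions about kinetics).** If the last sample of the interval is the highest, Cmax,tau = Cmin,tau, so PTFtau = 0 × 100 / Cav,tau = 0 and ln(PTFtau) is undefined. (If the end sample were not counted in the maximum, PTFtau would be negative, and its log equally undefined.) The ratio is safe: Cmax/Cmin,tau = 1 and ln(1) = 0.

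Three SAP provisions might be thought to repair this, and none does:
- 7.2.2 analyses observed cases and relies on the mixed model for missing data. These records would be missing because of their value.
- 7.2.8 looks for non-normal residuals. A dropped record has no residual.
- 7.2.9 leaves the scale for PTFtau open but does not choose one.

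**2. How often zeros might occur.** Assumptions: one-compartment superposition of four doses every 3.5 h on the protocol's sampling times; half-life 2 h; 25% variability on absorption rate, 15% on half-life, 5-10% residual noise. Share of first intervals with PTFtau = 0:

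| Assumed profile | First interval |
|---|---|
| IR, ka 3/h | 0% |
| MR, ka 0.7/h, no lag | 1-4% |
| MR, ka 0.7/h, lag 0.5 h | 7-12% |
| MR, ka 0.6/h, lag 0.75 h | about 26% |

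Across the first-order MR settings tried, the range is about 1% to 29%. For ka 0.6-0.8/h with a lag of 0.5-0.75 h, it falls to about 0-9% in interval 2 and 0-5% in intervals 3 and 4.

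**3. Near-zero values that survive.** A noise-free MR profile (half-life 1.5 h, ka 0.4/h, lag 1.5 h) gives PTFtau of 0.0, 0.6, 2.8 and 3.3% in intervals 1 to 4. The first is lost. The second and third differ by 2.2 percentage points, but on the log scale by ln(2.8/0.6) = 1.54, a factor of 4.7.

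**4. Effect of the trough definition.** PTFtau (%) in interval 2, half-life 1.5 h, IR ka 3/h, MR ka 0.7/h:

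| Profile | With Cmin,tau | With Cmin,tau,actual | Understated by |
|---|---|---|---|
| IR, lag 0 | 101.3 | 101.3 | 0% |
| IR, lag 0.5 h | 89.7 | 102.6 | 1 − 89.7/102.6 = 13% |
| MR, lag 0 | 40.0 | 40.0 | 0% |
| MR, lag 0.5 h | 28.8 | 41.2 | 1 − 28.8/41.2 = 30% |
| MR, lag 1 h | 17.2 | 42.6 | 1 − 17.2/42.6 = 60% |

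At an equal lag of 0.5 h the missed fall is almost the same in points (102.6 − 89.7 = 12.9 for IR; 41.2 − 28.8 = 12.4 for MR), but it is a larger share of the smaller MR value. Over half-lives of 1.5-2.5 h and intervals 1-3, the understatement at that lag is about 12-17% for IR and 28-57% for MR. With an MR lag of 1 h and no IR lag, the MR/IR ratio is 17.2/101.3 = 0.17 with Cmin,tau and 42.6/101.3 = 0.42 with the actual trough.

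**5. Interval 4.** Against the plan's 16 h trough, every arm changes. With half-life 2 h and no lag, IR goes from 76.9 to 106.6. Over half-lives of 1.5-2.5 h, the gap is 22-32% for IR without lag and 47-54% for MR without lag.

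**The case against.** A reader might infer that the end-of-interval trough favours MR by construction, understating MR fluctuation and leaving Sinemet untouched. The documents do not support that. The definition is the same for every arm, and neither document gives a lag, a tmax or a profile for either product. With an MR lag of 0 or 0.25 h there is no understatement in intervals 1-3 (half-life 2 h, interval 2: 28.9 and 23.3 with either trough). With an IR lag of 0.5 h, Sinemet is understated too (65.3 against 76.9). If only the IR tablet had such a lag, the distortion would run the other way. This objection stands.

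Three further objections carry weight:
- For the ratio, the actual-trough analysis is already planned, with its own SAP tables. What is missing is only its place among the main variables, a label with no significance level or decision rule attached. That list also contains Cmax/C(16h) and PTF0-16, which do not use the end-of-interval trough.
- PTFtau is neither primary nor secondary, and the MR-Sinemet contrast exists only in Group 4.
- Simply replacing the trough would create a new problem. In interval 4 it would pair a value 5.5 h after the dose with an average over 3.5 h, so PTFtau would jump in every arm and not compare across intervals.

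None of this supplies a rule for zeros. The SAP's open wording on transformation leaves the protocol's general log rule as the only instruction that covers PTFtau.

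**Conclusion.** The point holds in two parts. First, by definition alone, PTFtau is 0 when an interval ends on its highest sample, and the log analysis then loses that record. This can happen in any MR arm, mainly in the first interval, and is not expected for a fast IR tablet. The frequency, from about 1% to 29% of first intervals, rests wholly on assumed first-order kinetics and noise. Second, PTFtau lacks the actual-trough version that the ratio has. At an equal assumed lag of 0.5 h or more the understatement is proportionally larger for MR, but IR is not exempt, and with little or no lag there is none in intervals 1-3.

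The two effects pull in opposite directions for MR: dropping zeros raises its apparent fluctuation, and the end-of-interval trough lowers it. They cannot be relied on to cancel, so no net direction can be claimed. AUC0-24 is unaffected. The change is worth making because PTFtau is a named main variable and the repair is cheap.

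**What to change.** In SAP 8.4, with Protocol Table 4 and 8.4.3 aligned or the departure recorded under SAP 8.7:

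1. Analyse PTFtau on the original scale, with the same by-interval mixed model, so that zeros stay in. Report treatment differences with 90% CIs.
2. Add a PTFtau based on Cmin,tau,actual for intervals 1-3, beside the existing version. For interval 4 keep only the existing version, so that the 16 h trough is not paired with the 3.5 h average. Note that in intervals 1-3 the actual trough may lie slightly outside the AUCtau window, which is a reason to show both.
3. Add Cmax/Cmin,tau,actual to the list of main PK variables of interest.

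The cost is one derivation and one more set of table output. PTFtau contrasts would be differences in percentage points and not geometric mean ratios, and so less directly comparable with log-scale results for the other variables. No extra samples or subjects are needed.
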